- Determine the incidence, severity and etiologies of med errors and adverse drug events in kidney transplant recipients and compare these between the intervention and control cohorts.

C2 Secondary Aims

- Measure the total resources utilized (hospital, outpatient, staff effort) to provide care and compare these between the intervention and control cohorts.
- Measure the impact of med errors and adverse drug events on clinical outcomes, including acute rejections, infections, graft loss and death (exploratory aim)

D Study Design

D1 Overview or Design Summary

TRANSAFE Rx is a 12-month, parallel two-arm, 1:1 randomized controlled clinical trial, involving 136 participants (68 in each arm) and measuring the clinical and economic effectiveness of a pharmacist-led intervention, which utilizes an innovative mHealth application to improve medication safety and health outcomes, as compared to usual post-transplant care. The planned study design and interventions of this project were developed from the aforementioned foundational studies. These preliminary studies provided insight into interventions that were clinically effective, efficiently implementable, had a high-rate of patient acceptability and were capable of being scalable to a wide-array of patient populations. It is within this framework that the investigators have designed the TRANSAFE Rx study.

D2 Subject Selection and Withdrawal

2.a Inclusion Criteria

- 1) Kidney transplant recipient between 6 and 36 months post-transplant
- 2) At least 18 years of age
- 3) Transplant MD agrees that patient is eligible to participate

2.b Exclusion Criteria

- 1) Multi-organ recipient
- 2) Patient is incapable of:
 - a. Measuring their own blood pressure
 - b. Measuring their own glucose (if subject has diabetes)
 - c. Self-administering medications
 - d. Speaking, hearing and reading English
 - e. Utilizing the mHealth application, after training

2.c Ethical Considerations

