Ethical considerations for randomized, controlled trials include informed consent, risk of harm by the intervention, and risk of loss of confidentiality. Subjects eligible for this study will undergo an informed consent process with a study coordinator that is trained in the process and has completed the Collaborative IRB Training Initiative (CITI) offered online by the University of Miami. The PI of the study will be available for any questions and the subject will be provided adequate time to make an informed decision, as described in section 2(c). Because the intervention is technological, the greatest additional risk to the subjects is loss of confidentiality. Only data that is necessary for the purpose of the study will be collected. Subject data will only be available on password-protected devices and only encrypted data will be transferred.

Protection of Human Subjects: MUSC researchers are allowed the privilege of working with human subjects under normal assurance to the government that such research complies with regulations protecting human subjects. The university has a federal-wide assurance for research with human subjects and is in compliance with federal policy governing use of human subjects. Investigators involved in human subject research at MUSC are required to complete the Collaborative IRB Training Initiative (CITI) offered online by the University of Miami. In addition, all human subject protocols are reviewed through the MUSC Institutional Review Board (IRB). The Office of Research Integrity coordinates the activities of three IRB committees, involving faculty members as well as representatives in the legal, ethical, religious, civic, and business communities.

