Compliance: The MUSC University Compliance Program is a proactive program to ensure full agreement with all applicable policies, procedures, laws and regulations. This involves a confidential Compliance Helpline to encourage all members of the MUSC community to ask questions or voice concerns about laws and regulations on such topics as coding and billing, research integrity, professional ethics, human subjects, animal research, biological safety, conflict of interests, and patient confidentiality. The program office proactively trains employees and facilitates discovery of concerns, followed by appropriate investigation into problem areas and timely resolution of issues. This program directly assists MUSC's management at all levels in maintaining and enhancing an environment where ethics are paramount considerations in strategic and operational decisions throughout the organization.

2.d Subject Recruitment Plans and Consent Process

Subject Identification/Recruitment:

Adult (≥ 18 years old at the time of transplant) solitary kidney transplant recipients 6 to 36 months post-transplant that meet study eligibility will be identified through review of patients visiting the kidney transplant clinic as part of usual care and approached by research personnel for consideration for participation.

Informed Consent:

Authorized research personnel will approach patients to explain the study and offer the opportunity to participate in the study. The personnel who will obtain consent will have completed Human Subjects Protection Training. This research study will be explained in

lay terms to each potential research participant. In compliance with the informed consent process outlined in CFR Title 21 Part 50, the authorized personnel will conduct a face-to-face meeting with the study candidate to review all of the required elements of informed consent. The potential study participant will sign an informed consent form before undergoing any screening study procedures. The original consent form will be kept with the subject's file in the office. A copy of the consent will be given to the patient and another copy will be put in his/her chart. At the time of consent, patients will be assured that their care will not be affected in any way if they choose not to participate in the study. Patients will also be reminded that it is their right to withdraw their participation in the study at any time.

2.e Randomization Method and Blinding

Randomization Method:

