Whether a patient is in the intervention group or the control will be by random selection using a random number generator in a simple blocked manner (blocks of 8).

Blinding:

This is an open-label study, so subjects and the research team will be aware of the study assignment. Due to the nature of the intervention, blinding of the subject and research staff is unable to be performed. In order to minimize bias, data for outcomes will be collected by a blinded study coordinator.

2.f Risks and Benefits

There are minimal risks to patient safety during the completion of this study within the intervention arm and no risks with regards to study interventions within the control arm. This study will not involve requiring patients to take any experimental medications. All patients, regardless of randomization will receive standard usual care as part of this study. Any adjustments or changes made to the patient's medication regimen in the intervention group will be approved by a transplant physician. There will be increased monitoring and scrutiny of patient's home blood pressures, glucoses and medication regimens. All documented medication errors and adverse drug events will be identified by a blinded research coordinator at the same frequency and methodology across intervention and control patients. This will minimize the likelihood of identifying higher rates of medication safety issues in the intervention group. The risk associated with the intervention arm is in loss of patient confidentiality, which will be mitigated through the use of HIPPA compliant data encryption on mobile devices and storage of PHI on password protected databases behind the MUSC firewall.

Although it is expected that this will improve medication safety, it may also increase stress on patients and increase the potential of identifying false positive information. We will minimize the risk of this causing harm to study patients by ensuring all data is closely monitored by a highly trained clinical pharmacist. All interventions made based on this will be reviewed and approved by a transplant physician.

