Home-based monitoring of blood pressures and glucoses, using the FORACare system, will also transfer into the application and the report dashboard.(42, 43) The app will also give providers the ability to create and send surveys to the patient. The survey will populate on the patients' home screen as an alert message. The alert message will not disappear until the survey has been filled out and submitted. Survey responses get recorded in the app and are incorporated into the report dashboard. As part of this study, patients in the intervention cohort will receive medication side effect surveys during gaps in transplant clinic visits. The survey was developed using the validated Memphis Medication Side Effect Survey, coupled with our formative research demonstrating which side effects are associated with the adverse drug events that are most commonly associated with hospital readmission.(44-46) Patients will complete this survey and this data will then flow into the report dashboard for review as aggregate and trend information. Thus, this mHealth system will allow both the patient and transplant pharmacist to track signs and symptoms of medication safety issues.

3.b Method for Assigning Subjects to Treatment Groups

Whether a patient is in the intervention group or the control will be by random selection using a random number generator in simple blocks of 8.

3.c Subject Compliance Monitoring

Monitoring for compliance with medications, clinic visits, blood pressure and glucose monitoring (if applicable) is a part of the intervention in the intervention cohort. If subjects are not complying with data monitoring in the intervention cohort, they will be contacted by the study pharmacist to encourage use of the smartphone and any relevant Bluetooth-enabled devices. If this does not resolve the noncompliance, the subject will be contacted by the study PI to discuss continued involvement in the study. These data will not be monitored real-time in the usual care cohort. Compliance with study data capture will be monitored by the study coordinators, who are completely independent of the pharmacists providing the interventions. They will gather data via direct subject interview and through review of the subject's electronic medical records.

3.d Blinding of Study Intervention

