To assess for adverse drug events, the research coordinator will review patient symptomology, vital signs and laboratory values. The research coordinator will be trained by the study pharmacists in identifying medication errors and adverse drug events, determining causality and grading the severity. To ensure objectivity and consistency in recording these events across both study cohorts, a number of safeguards will be instituted. First, the study investigators will utilize the same research coordinator to record all medication errors and adverse drug events. Second, this research coordinator will be completely independent of the telehealth intervention that is being performed and will be blinded to the patient’s randomized group. Third, only the medication errors and adverse drug events recorded by this research coordinator will be

used for data analysis. Finally, these patient assessments will be followed by an independent assessment by a clinical transplant pharmacist that is not associated with delivering the study intervention. This will ensure that event rates are not biased towards a higher capture rate in the intervention cohort, which will be receiving more intense scrutiny of their medication regimens by a clinical pharmacist.

E4 Study Outcome Measurements and Ascertainment

The primary outcome measure of this study will be the incidence and severity of medication errors and adverse drug events, which will be identified, categorized and compared between the intervention and control cohorts as detailed above and in the following sections. The exploratory outcome measures of this study are to compare the incidence and severity of acute rejections, infections, graft function, graft loss and death between research cohorts and measure the association between medication safety issues and these events. Demonstrating improvements in acute rejections, infections, graft loss or death within the intervention group will provide the data needed to design a larger, multicenter study (through dissemination efforts detailed at the end of this proposal). Additional data that will be gathered includes patient surveys to capture measures of sociodemographics, health literacy, depression, social support and trust. These are important variables that may modify or confound the impact of the intervention.

Study endpoint definitions and assessment plan:

The following will be used to define and capture data and events within this study:

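### A single fixed block size of 8 in an open-label, single-centre trial, with no described concealment of the next assignment, leaves avoidable scope for selection at enrolment

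*Combined protocol and SAP*

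**What the plan says.** Section D2 2.e assigns patients by "random selection using a random number generator in a simple blocked manner (blocks of 8"). Section D3 3.b repeats this as "random selection using a random number generator in simple blocks of 8". Neither section names strata, a second block size, a holder of the list, or a procedure for releasing an assignment.

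The same section 2.e states that "subjects and the research team will be aware of the study assignment". H1 gives one participating centre, so there is one allocation sequence.

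Enrolment runs through staff at that centre. Under 2.d, patients seen in clinic are "approached by research personnel for consideration for participation". Under 2.c they "undergo an informed consent process with a study coordinator". Inclusion criterion 3 in 2.a is "Transplant MD agrees that patient is eligible to participate". Section E2 places screening, consent and randomisation at one baseline visit.

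The plan's safeguards concern measurement. Section 2.e says "data for outcomes will be collected by a blinded study coordinator", and E3 3.e adds that "this research coordinator will be completely independent of the telehealth intervention", with later adjudication by a pharmacist who does not deliver the intervention. Section F3 analyses all randomised patients as assigned and provides model-based adjustment if baseline characteristics are significantly imbalanced.

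**The concern.** Within a 1:1 block of 8, once four patients have gone to one arm, the rest of the block is fixed. Anyone who knows the block size and has followed the assignments can then name the next arm with certainty. At other points they can guess better than chance by backing the arm that is behind.

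There is room to act on such knowledge. Patients are eligible from 6 to 36 months after transplant and are approached at routine visits, so an approach can be deferred. The physician's agreement is a matter of judgement. Assignments are visible because the intervention arm receives monitoring devices and the app. The H5 targets, 136 patients from 15 October 2017 to 31 March 2019, imply about 136/17.5 = 7.8 patients a month, or roughly one block a month in one clinic.

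At stake is the comparability of the arms. Section B1 attributes most medication errors to unintentional non-adherence, and clinic staff may already have a view of which patients are prone to it. If such patients were steered towards one arm, blinded outcome recording and intention-to-treat analysis would faithfully measure a comparison that was already unbalanced.

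**Working it through.** The plan gives no figure for predictability, so there is none to reproduce.

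**Inputs.** Block size 8 (2.e, 3.b); 1:1 allocation, 136 patients, 68 per arm (D1). 136/8 = 17 complete blocks.

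**Step 1: all past assignments and the position in the block known.** There are C(8,4) = 70 equally likely sequences. The certain assignments in a block are those in its final run of identical assignments. The chance that this run has length at least k is 2 × C(8−k, 4)/70:

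- k = 1: 2 × 35/70 = 1.000
- k = 2: 2 × 15/70 = 0.429
- k = 3: 2 × 5/70 = 0.143
- k = 4: 2 × 1/70 = 0.029

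The sum is 1.6 certain assignments per block. So 1.6/8 = 20.0%, and 17 × 1.6 = 27.2 of 136.

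This is an average. A single block has 1, 2, 3 or 4 certain assignments with probability 57.1%, 28.6%, 11.4% and 2.9%, so 12.5% to 50% of the block. Over 17 simulated blocks the 95% range was 21 to 34 patients (15% to 25%).

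Always guessing the arm that is behind, and tossing a coin when the arms are level, is right 4 + 2^7/70 − 0.5 = 5.33 times in 8, or 66.6%.

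**Step 2: only some past assignments known.** If j earlier assignments in the block have been seen and a of them were intervention, the chance that the next is intervention is (4−a)/(8−j). It is certain only when all four assignments to one arm have been seen. Averaging over positions, with each past assignment seen independently with probability q:

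| q | Certain | Best guess right | 2g − 1 |
|---|---|---|---|
| 1 | 20.0% | 66.6% | 0.332 |
| 0.75 | 6.3% | 60.9% | 0.219 |
| 0.5 | 1.25% | 57.5% | 0.150 |
| 0.25 | 0.1% | 54.4% | 0.087 |
| 0 | 0% | 50% | 0 |

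**Step 3: what steering could do.** Let g be the proportion of correct guesses, and suppose every guess is acted on. A share g of each arm is then the type of patient steered towards it and 1 − g is the other type. The arms' baseline risks differ by (2g − 1) times the risk gap between the two types (last column). The documents give no such gap, so this cannot be turned into percentage points of medication errors.

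**Step 4: varying block sizes.** Take 5 blocks of 6, 7 of 8 and 5 of 10 in random order: 30 + 56 + 50 = 136, and 15 + 28 + 25 = 68 per arm. In simulation with all past assignments known, about 1.5% of assignments are certain if the observer does not know the mix of sizes and about 2.8% if he does. That is roughly 2 to 4 of 136 patients. The best guess is still right about 66% of the time.

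**The case against.** Five points can fairly be made on the other side.

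First, a reader might take 20% as the share of assignments that will be known, or as a ceiling. It is neither. It is an average that requires full knowledge of past assignments and block position, and nothing in the documents says recruiters track the sequence. Section 2.c leaves open whether the coordinator who takes consent is blinded. This stands, and the range from 0% to 20% must be given with its conditions.

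Second, a reader might infer that allocation is not concealed. The text supports only that the two sections devoted to allocation describe no concealment. Not all attachments were available to this review (the modified grading scale that E3 3.c places at the end is absent, for example), so a procedure may exist elsewhere.

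Third, 8 is a fairly large block; a block of 4 would make 33% of assignments certain. By the best-guess measure, varying the block size gains almost nothing. Both statements are correct, and they show that controlled release matters more than block size.

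Fourth, F3 provides adjustment for baseline imbalance, and E4 plans to collect sociodemographics, health literacy, depression, social support and trust, which are plausible traits for steering. This helps with what is measured. It does not reach a clinician's unrecorded impression of a patient.

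Fifth, exclusion 2(e), inability to use the app after training, could be read as removing patients from the intervention arm after allocation, because E4 item 8 costs training to that arm only. The documents do not support that. The item is an entry criterion, E2 lists screening before randomisation, the costing text is not a schedule, and F3 keeps all randomised patients in the analysis. What remains is that the timing of the check is not stated.

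**Conclusion.** The concern holds as a potential selection-bias risk. The plan fixes one block size of 8 in an open-label, single-centre trial with a discretionary entry step, and the available text describes no concealment of the next assignment. The size depends on what recruiters know: from 20% certain and a 67% best guess with all past assignments known, through about 1% and 57% with half known, to 0% and 50% with none. Every case assumes that block size and position are known. No bias has been shown and none can be quantified from these documents. The existing safeguards protect outcome recording, or correct for measured characteristics after enrolment; none prevents foreknowledge. The change is worth making because it is cheap and cannot be applied retrospectively. The timing of exclusion 2(e) is a matter of clarification only.

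**What to change.** 1. Replace the fixed block of 8 with block sizes in random order, not disclosed to recruiters; for example 5 blocks of 6, 7 of 8 and 5 of 10.
2. Release each assignment through the existing study database (G1) only after consent, physician agreement and every eligibility item have been recorded. State who generates and holds the list; that person should not recruit. If a procedure outside these sections already does this, cite it in 2.e.
3. Do not give recruiters the running list of assignments.
4. State in 2.b or E2 that exclusion 2(e) is judged in every candidate before randomisation.

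The cost is a new list, a release step that fits within the single baseline visit, a few lines of protocol text, and a brief app check for patients later assigned to usual care. The total of 136 and 68 per arm are kept. If recruitment stopped early, the largest possible imbalance from an unfinished block would be 5 patients instead of 4.

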Importance of the Knowledge to be Gained

It is hoped that the information gained from the study will help the researchers learn more about the incidence, severity, root cause and potential outcomes associated with medication safety issues within kidney transplant recipients and determine if a pharmacist-led mHealth enabled intervention can potential reduce these events.

2.g Early Withdrawal of Subjects

If a study subject desires to prematurely terminate the study intervention, if possible, a visit will be scheduled with the Principal-Investigator (PI) or designee within seven days to evaluate the reason for early termination. It will be clarified whether they are terminating from all components of the trial or only from the primary intervention component of the trial. Ultimately, subjects have the autonomy to withdraw from the study or stop the intervention if they so desire.

2.h When and How to Withdraw Subjects

Subjects will complete the study at the end of the 12-month follow up period or at the time they wish to prematurely terminate the study.

2.i Data Collection and Follow-up for Withdrawn Subjects

If a study subject wishes to terminate the study intervention, but are willing to continue to report outcomes, they will have outcome data collected until their final study visit. If any subject wishes to terminate from all aspects of the study and withdraw, data collection will cease from that point on and outcomes will be censored at that point for data analysis.

D3 Study Intervention

3.a Treatment Regimen

[figure not shown]
Intervention Cohort

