6. Graft failure will be defined as return to chronic dialysis, transplant nephrectomy, retransplantation or death. The study coordinator capturing clinical event data, different from the coordinator capturing medication error and adverse drug event data (to ensure independence is maintained), will review the medical record at regular intervals to determine if a study patient has developed graft failure. The timing and cause of each graft loss will be recorded for comparative analysis. Patient death will also be captured in a similar fashion, with timing and cause recorded as well.

7. Healthcare encounters will be defined as any direct encounter (face-to-face) between the study patient and a physician or advance practice provider (APP) occurring within a licensed healthcare facility and occurring during the 12-month study. These encounters will be categorized as ambulatory clinic visits, ambulatory procedure visits, acute care/emergency room visits and hospitalizations. Hospitalizations will be defined as an admission to a hospital with at least one overnight stay. Length of stay within the hospital for readmissions will also be captured. Healthcare encounters will be captured through direct study subject interviews with patients at bimonthly intervals.(36) The study coordinator will record all healthcare encounters that have occurred. If the patient has a health care encounter outside of the study institution, the research coordinator will document the type of encounter to estimate costs, as detailed below.

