This analysis will incorporate the intent-to-treat principle, namely, all randomized participants will be included in the analysis according to their intervention assigned at baseline. The two groups will be compared using standard statistical analyses. Data will be reported using percentages for nominal and ordinal variables and compared using Fisher's exact test or Pearson's chi-squared test as appropriate. This includes baseline demographic and transplant characteristic variables, as well as the outcome variables of the incidence and severity of medication errors and adverse drug events, acute rejection and infections. For continuous variables with normal distribution, results will be reported using means and standard deviations with statistical comparison using Student's t-test for two independent samples. For *non-normally distributed* variables, the results will be reported using medians and interquartile ranges, with statistical comparison conducted using the Mann Whitney U test. Normal distribution of continuous variables will be assessed using normality plots and the Shapiro-Wilk test. Normal variance will be assessed using Levene's test for equality of variances. Results for graft and patient survival will also be reported using Kaplan-Meier survival curves and compared using the Log Rank test.

If it is determined that there are significant imbalances in baseline demographics or characteristics known to influence any of the outcome measures, multivariable modelling will be used to adjust for these differences. For nominal outcomes, binary logistic regression will be used in a standard entry fashion, which will include both the grouping variable and all known risk-factors. For continuous outcomes that demonstrate linearity

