in the relationship between dependent and independent variables, with a lack of serial correlation between covariates, homoscedasticity of the errors and normality of the error distribution, linear regression will be utilized in a similar manner. We will adjust for baseline values if the interventions are discrepant at baseline. This model will include the intervention arm and baseline response as fixed-effects and is known to lead to very precise inference.(7) If any of the four aforementioned assumptions are violated, then the data variables will either be transformed or appropriate substitute multivariable modelling will be used. Cox proportional hazard regression analysis will be used for time-dependent survival analyses involving the outcomes of graft and patient survival. For count outcomes, such as health care encounters, we will use Poisson regression; if the assumption of equal mean and variance is violated (over dispersion), we will use Negative Binomial regression. In all models, we will adjust for correlation of outcomes by including random effect terms. For all models that belong to the generalized linear model (linear, logistic, Poisson), we will use generalized estimating equations (GEE), and for survival outcomes, we will use frailty Cox regression.(8) We will use multiple imputation techniques to deal with missing data that is at random (MAR).(9) MAR assumes that the probability that an outcome is missing depends on observed outcomes. While mechanisms for missingness are likely to be MAR, we will also do sensitivity analysis for data missing not at random (MNAR) using methods from Little and Rubin.(9)

F4 Statistical Methods

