The two groups will be compared using standard statistical analyses. Data will be reported using percentages for nominal and ordinal variables and compared using Fisher's exact test or Pearson's chi-squared test as appropriate. This includes baseline demographic and transplant characteristic variables, as well as the outcome variables of the incidence and severity of medication errors and adverse drug events, acute rejection and infections. For continuous variables with normal distribution, results will be reported using means and standard deviations with statistical comparison using Student's t-test for two independent samples. For *non-normally distributed* variables, the results will be reported using medians and interquartile ranges, with statistical comparison conducted using the Mann Whitney U test. Normal distribution of continuous variables will be assessed using normality plots and the Shapiro-Wilk test. Normal variance will be assessed using Levene's test for equality of variances. Results for graft and patient survival will also be reported using Kaplan-Meier survival curves and compared using the Log Rank test.

F5 Missing Outcome Data

We will use multiple imputation techniques to deal with missing data that is at random (MAR).(9) MAR assumes that the probability that an outcome is missing depends on observed outcomes. While mechanisms for missingness are likely to be MAR, we will also do sensitivity analysis for data missing not at random (MNAR) using methods from Little and Rubin.(9)

F6 Unblinding Procedures

No unblinding procedures are necessary, as this is as open-label study.

G Data Handling and Record Keeping

G1 Confidentiality and Security

In order to protect subjects against any risk regarding loss of personal information, all obligations under the Health Portability and Accountability Act (HIPPA) will be met. Additionally, all data will be collected and stored through the secure network server and behind the MUSC firewall. We will use electronic CRF forms to gather all study information (redcap.musc.edu). Data will only be stored on campus computers under the MUSC secure network. Data collection forms will be maintained within an office, which is a locked office facility on campus. Only approved study members will have access to patient data.

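### Does censoring outcomes at full withdrawal leave the comparison of medication errors, adverse drug events and healthcare encounters open to bias?

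*Combined protocol and SAP*

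**What the plan says.** Section D2 2.i separates two kinds of withdrawal. For patients who stop only the intervention, "they will have outcome data collected until their final study visit". For patients who leave the study altogether, "data collection will cease from that point on and outcomes will be censored at that point for data analysis".

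Section F3 sets the analysis population: "all randomized participants will be included in the analysis according to their intervention assigned at baseline". Fisher's exact or Pearson's chi-squared test is assigned to nominal and ordinal variables, including "the outcome variables of the incidence and severity of medication errors and adverse drug events, acute rejection and infections". Kaplan-Meier, log-rank and Cox methods are named only for graft and patient survival.

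On encounters, F3 says "For count outcomes, such as health care encounters, we will use Poisson regression", with negative binomial regression if there is overdispersion. It also calls for adjustment for correlated outcomes in all models and for GEE in the linear, logistic and Poisson models. Section E4, item 7, gives the data structure: "Healthcare encounters will be captured through direct study subject interviews with patients at bimonthly intervals".

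Section F5, on missing outcome data, says "We will use multiple imputation techniques to deal with missing data that is at random (MAR"), and adds a sensitivity analysis for data missing not at random (MNAR). Section F1 expects 85% retention and gives no split by arm and no timing.

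**The concern.** Censoring is a survival-analysis idea, and the tests named for the primary outcomes are not survival methods. A patient who leaves event-free at month 2 could be coded as a 12-month non-event, dropped or imputed, and no sentence ties 2.i to one of these. The encounter model states neither its unit (a 12-month total or a two-month interval) nor an offset for time observed. Costs raise a similar question: E4 item 8 runs hospital-accounting costs to month 12, while 2.i stops data collection at full withdrawal.

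If shorter follow-up were read as fewer events, the arm that lost more patients, or lost them earlier, would look better. Only the intervention arm carries app check-offs, device readings and calls about non-compliance, so unequal loss is conceivable. For Hypothesis 2 the planned difference is only 1.4 encounters, and a shift of about one encounter would matter.

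**Working it through.** **Inputs from F1.** Control error incidence 64%, halved to 32% by the intervention; grade 3 or higher adverse drug events (ADEs) 87% in control; encounters 18.4 (SD 2.6) against 17.0; 52 evaluable per arm; 68 randomized per arm; 15% loss overall. **Assumed:** the split of loss between arms, its timing, that all loss is full withdrawal, a constant event hazard, and withdrawal unrelated to outcome.

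**1. The plan's own figures.** Errors: the pooled standard error is √(2 × 0.48 × 0.52 / 52) = 0.0980 and the unpooled one is √((0.64 × 0.36 + 0.32 × 0.68) / 52) = 0.0928. Then (0.32 − 1.96 × 0.0980) / 0.0928 = 1.38, which is 91.6% power (stated: 92%). Encounters: 1.4 / (2.6 × √(2/52)) − 1.96 = 0.79, which is 78.4% (stated: 80%).

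**2. Errors and ADEs with withdrawals coded as non-events, no true effect.** With H = −ln(1 − p) and withdrawal uniform over the year, a withdrawn patient has an observed risk of 1 − p/H.
- Errors: H = 1.0217, so 1 − 0.64/1.0217 = 0.3736.
- ADEs: H = 2.0402, so 1 − 0.87/2.0402 = 0.5736.

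The observed risk in an arm losing a share w is (1 − w)p + w(1 − p/H). Type I error comes from exact enumeration of the chi-squared test with 68 per arm.

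| Loss, control/intervention | Errors observed | Shift | Type I error |
|---|---|---|---|
| 15% / 15% | 60.0% v 60.0% | 0 | 4.8% |
| 10% / 20% | 61.3% v 58.7% | 2.7 points | 6.0% |
| 5% / 25% | 62.7% v 57.3% | 5.3 points | 9.4% |

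Reversing a split reverses the sign. A milder 12/18 split gives 0.06 × (0.64 − 0.3736) = 1.6 points, type I error 5.2%. For ADEs, 10/20 gives 3.0 points (7.3%) and 5/25 gives 5.9 points (14.7%). With equal 15% loss but control leaving at month 10 and intervention at month 2, errors shift by 6.2 points (11.2%).

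The planned 32-point effect on errors would be seen as 30.2 (15/15), 32.3 (10/20) or 28.2 (20/10).

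**3. The same outcomes as F3 and F5 would have them.** With withdrawals multiply imputed (6,000 simulated trials per split, 20 imputations from an exponential model per arm), the difference under no effect stays within 0.2 points of zero, with type I error 4.7% to 5.4%. Excluding all withdrawals performs the same; about 68 × 0.85 = 57.8 per arm remain, and 57 per arm still gives 93.8% power for errors.

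**4. Encounters as 12-month totals without an offset.** The observed mean is m(1 − w/2).
- 10/20, no effect: 18.4 × 0.95 = 17.48 against 18.4 × 0.90 = 16.56, a false difference of 0.92; type I error about 16% in simulated Poisson trials.
- 5/25: 17.94 against 16.10, a false difference of 1.84; 47.7%. With the plan's smaller SD of 2.6 and withdrawal fixed at month 6, the same 1.84 gives 75.8%.
- Planned effect: 10/20 shows 17.48 − 17.0 × 0.90 = 2.18; 20/10 shows 16.56 − 17.0 × 0.95 = 0.41.

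**5. Encounters by observed two-month interval, or with a log(months) offset.** The false difference is 0.00 and type I error is 5.1% to 5.4%.

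**6. Which reading the text supports.** Section 2.i says collection stops, so later outcomes are absent, which is what F5 addresses. F3 retains every randomized patient, which rules out dropping withdrawals as the main analysis. Censoring means that status afterwards is unknown, whereas coding a non-event claims that it is known. In a single-center, individually randomized trial, correlated outcomes most naturally means repeated records within a patient, and E4 supplies those every two months.

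**The case for a change.** The strongest case for a change is that censoring and imputing are different instructions and the plan never connects them. In an open-label trial, leaving the choice until arm-level data are visible invites a result-dependent decision. Section D3 3.c gives a route out that exists only in the intervention arm: persistent non-compliance with monitoring leads to a conversation with the principal investigator about staying in the study. For encounters the consequence of the wrong choice is large against a planned 1.4. The remedy would take a few sentences.

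Part of this stands. The linking sentence is absent, the unit of the count model is not named, and the position on costs after full withdrawal is not stated.

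The rest is weaker. Non-event coding is not on an equal footing with imputation, because it runs against both the word used in 2.i and F5. The large encounter figures need a single total with no exposure term, which fits poorly with GEE and two-monthly capture. Patients tired of the app can stop the intervention and stay in follow-up under 2.i, so the burden need not turn into full withdrawal. No split or timing is documented, and the 5/25 and month-10-against-month-2 scenarios are illustrations only. The cost question partly depends on what patients consented to, and nothing in the documents allows it to be sized.

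**Conclusion.** No change to the plan follows. Read together, 2.i, F3 and F5 lead to a sound analysis: status after full withdrawal is missing, it is imputed for all randomized patients, and the MNAR analysis tests the result. Encounter counts taken by observed interval carry their own time at risk. Under those readings the error difference stays within 0.2 points of zero, the encounter difference is 0.00, and type I error is near 5%.

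Bias appears only under readings that the plan does not state. At an assumed 10/20 split it is 2.7 points for errors (small beside a planned 32) and 0.92 encounters (two-thirds of the planned 1.4). Equal, equally timed withdrawal creates no false difference under any reading. What remains is missing detail that a competent analyst supplies when programming the analysis.

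The conclusion assumes that withdrawal is missing at random or non-informative. If it is informative, neither imputation nor an offset removes the bias, and the planned MNAR analysis is the safeguard.
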